2.1 Primary outcome variables

The primary symptom outcome variables include self-reported Nasal Obstruction Symptoms Evaluation (NOSE) score and VAS of nasal obstruction.

The primary independent objective variables include several categories: 1) variables that index general disease severity (Computerized Tomography (CT) staging and endoscopic examination score), 2) peak inspiratory flow measurements of nasal physical resistance.

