2.2 Secondary outcome variables

Secondary outcome variables will include age, gender, race, duration of the disease, and medical and smoking histories. The potential confounding effect of the secondary outcome variables will be examined.

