3. Research CT scans: The subject may receive a CT scan for non-clinical purposes with a cone beam office CT scanner (3D Accuitomo 170, J. Morita USA, Inc.) at the Department of Otolaryngology at The Ohio State University School of Medicine. This scan has a radiation dosage of roughly 12% that of a conventional head CT scan with a significantly lower associated health risk, while retaining excellent air-mucus contrast for CFD modeling. The recruitment strategy will reduce the need for research CTs and unnecessary radiation by recruiting patients who have been prescribed a sinus CT clinically, which will serve as the subject's baseline CT. Furthermore, if a post-treatment/surgery CT scan is clinically necessary for a patient after enrollment, it will be scheduled for the subject's second study visit. Through these measures, the need for research CT scans will be reduced to limit the number of research CT scans for all patients to one (1).
4. CFD Modeling: 3D numerical nasal models that are suitable for numerical simulation of nasal airflow and odorant transport will be constructed based on each subject/patient's CT scan and according to the method described by Zhao⁸. In brief, first the interface between the nasal mucosa and the air is delineated (using AMIRA[®]) on the CT scans. Then, the nasal cavity air space is filled with tetrahedral elements (ICEMCFD[®]). A finer mesh (prism layer) is created near the mucosal surface to more accurately model the rapidly changing near-wall air velocity and odorant concentration. Next, inspiratory and expiratory quasi-steady laminar nasal airflow^{8,9} is simulated (Fluent[®], Ansys Inc, USA) by applying a physiologically realistic pressure drop between the nostrils and the nasal pharynx. By varying the pressure drop and computing the changes in total airflow through the nose, the total nasal resistance can be determined, a numerical method of rhinomanometry. Through simulation, the following variables will be obtained: numerical nasal resistance, nasal mucosal cooling rate, and nasal airflow distribution patterns.

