4.8 Internal Validity

The participating physicians will ensure that the recruitment material is well distributed to all potential subject/patient populations. In the recruitment process, they will specifically emphasize to all potential subjects/patients that whether or not they agree to participate will not have any impact on their continuing treatment and interactions at the Department of Otolaryngology, The Ohio State University School of Medicine.

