4.9 Data Analysis

Treatment effectiveness

Outcome variables: patient's ratings of nasal obstruction via a VAS and NOSE score as well as the SNOT-22 questionnaire and peak inspiratory flow rate. One-way ANOVA with repeated measures will be used to compare post-treatment vs. baseline measurements and determine the effectiveness of the treatment.

Hypothesis:

Nasal valve region airflow and airflow induced cooling is critical for patients' subjective nasal patency.

Many publications suggest that sensory feedback is as important to perception of nasal obstruction as nasal resistance. For example: Topical or oral application of menthol produces the illusion of decongestion and improved nasal airflow without actually altering nasal resistance¹⁰. Topical application of local anesthetics results in an artificial sensation of nasal obstruction, presumably due to blocking of the trigeminal afferents¹¹.

The Ohio State University (OSU) staff have published a series of studies^{6,12,13} with individualized Computational Fluid Dynamics models and demonstrated that nasal cooling during breathing at the nasal valve region and the nasal trigeminal nerve sensitivity are key to the perception or absence of nasal obstruction. The combination of these variables can predict the subject's ratings (excellent, normal and moderately obstructed) with 89.3% success. It is likely that nasal valve width and shape may have an optimal range in order to achieve both low nasal resistance and high regional mucosal cooling (see Fig. 5). This study will examine a broad list of factors that may contribute to patients' subjective outcomes, not just limited to nasal resistance alone, that include CFD simulation of nasal airflow, mucosa cooling and mucosa sensitivity responding to that cooling.

[figure not shown]

Figure 5. Computational simulation of nasal cooling

- a) high regional cooling, no complaints
- b) low nasal cooling with moderate ratings of nasal obstruction

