Spearmen correlation and multiple regression will be used to screen for independent variables that significantly correlate with dependent variables, as well as potential non-linear relationships between the variables. Other potential confounding factors (e.g., age, duration of the disease, smoking history) will also be examined. The Holm Bonferroni correction will be applied to control for multiple comparisons. Finally, statistical learning methods such as linear discrimination analysis (LDA) and logistic regression will be applied for classification and discrimination of patient symptom categories (e.g., symptom-free, moderate and severe nasal obstruction) based on significant independent variables.

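### Symptom categories are to be classified from predictors screened in the same 20 or fewer subjects, with no validation planned; a resubstitution accuracy would on average read too high whenever a predictor is selected

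*Combined protocol and SAP*

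**What the plan says.** Section 4.9 (Data Analysis) sets out three steps.

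1. Screening: "Spearmen correlation and multiple regression will be used to screen for independent variables that significantly correlate with dependent variables". The same sentence extends the screen to non-linear relationships.
2. Multiplicity: "The Holm Bonferroni correction will be applied to control for multiple comparisons". The alpha level and the number of tests are not stated.
3. Classification, by methods such as LDA and logistic regression: "classification and discrimination of patient symptom categories (e.g., symptom-free, moderate and severe nasal obstruction) based on significant independent variables".

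Section 4.2 caps recruitment at 20 and describes no second sample. No section plans a hold-out set, cross-validation, bootstrap correction or external validation. Section 4.8 is titled Internal Validity but concerns recruitment: "The participating physicians will ensure that the recruitment material is well distributed to all potential subject/patient populations".

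Section 2.0 makes prediction of treatment outcome an aim. Section 4.9 cites 89.3% success for earlier models on a different set of rating categories. It does not name a performance measure for this trial, does not say which visit's category is to be classified, and does not define the categories beyond an example.

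**The concern.** Selection and fitting use the same few subjects. A predictor passes only if its sample association with the outcome is large, and part of that association is chance. A rule built on it and scored on those same subjects counts the chance part twice, once in selection and once in fitting. New patients do not share that chance part.

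At stake is the prediction aim of section 2.0, which is meant to support personalised treatment planning. A reader of the final report could take a same-data percentage as the accuracy to expect in the next patient. The usual shortcut, leave-one-out run only after the variables have been chosen, would not fully protect against this, because the held-out subject has already helped to choose them.

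**Working it through.** The plan gives no accuracy or power calculation for this step, so there is no figure of its own to reproduce. The 89.3% comes from cited work and cannot be rebuilt from the documents.

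**Inputs from the documents**
- Sample size: up to 20 (section 4.2).
- Objective candidates in section 2.1: "variables that index general disease severity (Computerized Tomography (CT) staging and endoscopic examination score), 2) peak inspiratory flow measurements of nasal physical resistance", counted as 3.
- Airflow-model candidates in section 4.6: "numerical nasal resistance, nasal mucosal cooling rate, and nasal airflow distribution patterns", counted as 3. Subtotal 3 + 3 = 6.
- Section 4.9 adds mucosal sensitivity in "CFD simulation of nasal airflow, mucosa cooling and mucosa sensitivity responding to that cooling" (1 more), and section 2.2 adds "age, gender, race, duration of the disease, and medical and smoking histories" (6 more). Total 6 + 1 + 6 = 13.

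These are minimum-style counts. Airflow patterns, for instance, could yield several variables.

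**Assumptions not in the documents**
- Standard normal, independent predictors, one of them real with correlation rho to a continuous symptom score, and the score cut into three equally likely classes.
- Screening on the same score that is then classified. Section 4.9 does not define its dependent variables, so this is an inference.
- Spearman p-values, Holm at two-sided 0.05, LDA on the survivors.

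**What selection requires at n = 20**
The first Holm step needs p ≤ 0.05/m. With 18 degrees of freedom and r = t/√(t² + 18):
- m = 6: p ≤ 0.0083, t ≥ 2.96, r ≥ 2.96/√(8.78 + 18) = 0.57.
- m = 13: p ≤ 0.0038, t ≥ 3.32, r ≥ 3.32/√(10.99 + 18) = 0.62.

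The first variable selected must therefore show a sample correlation of about 0.57 to 0.62 or more, even if its true correlation is 0, 0.3 or 0.5.

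**What Holm does control**
With no real predictor, the chance of any selection is about 1 − (1 − 0.05/6)^6 = 0.049 for 6 candidates and 1 − (1 − 0.05/13)^13 = 0.049 for 13. The simulated rate is 5-6%.

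**Simulation**
Each simulated study was screened and LDA was fitted on the survivors. Four accuracies were averaged over studies in which something was selected: resubstitution, leave-one-out after the screen, leave-one-out with the screen inside each fold (nested), and accuracy in new subjects. Ranges cover 6 and 13 candidates.

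| rho | Something selected (6 / 13) | Resubstitution | Leave-one-out after screen | Nested | New subjects |
|---|---|---|---|---|---|
| none | 5-6% | 60-62% | 49-51% | 39-40% | 33% |
| 0.5 | 34% / 26% | 63-64% | 53-54% | 46% | 45% |
| 0.7 | 76% / 68% | 66-67% | 57% | 52-54% | 54% |
| 0.9 | about 98% or more | 77-78% | 70% | 69-70% | 70% |

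Resubstitution minus new subjects, in points:
- No real predictor: 60 − 33 = 27 to 62 − 33 = 29 (26-29 over repeat runs).
- rho 0.3 (selected in about 10-11% of studies): 23 with 6 candidates, 25 with 13.
- rho 0.5: 63 − 45 = 18 to 64 − 45 = 19 (16-20 over repeat runs).
- rho 0.7: 66 − 54 = 12 to 67 − 54 = 13.
- rho 0.9: 77 − 70 = 7 to 78 − 70 = 8.

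Leave-one-out after the screen minus new subjects:
- No real predictor or rho 0.3: 13-18.
- rho 0.5: 53 − 45 = 8 to 54 − 45 = 9 (6-10 over repeat runs).
- rho 0.7: 57 − 54 = 3.
- rho 0.9: 70 − 70 = 0.

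Nested minus new subjects:
- No real predictor: 39 − 33 = 6 to 40 − 33 = 7 (up to 8 in repeat runs).
- rho 0.3: +4.6 with 6 candidates, +4.8 with 13 (standard error 0.5).
- rho 0.5 to 0.9: within about 3 points either way.

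**Other settings**
With 10 or 20 candidates, none, two or three real predictors, and two or three classes, the excess of resubstitution over new-subject accuracy under Holm was 6 to 29 points, always in the same direction on average. Resubstitution was the higher figure in about 80% to 100% of single studies, so the bias is one of averages and not of every data set.

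**The case against.** **The harm is conditional.** Section 4.9 commits to classification, not to an accuracy figure. The 89.3% is background on other categories and does not show what this trial will report. Section 2.0 speaks only of an attempt, in a small case series. This stands and limits the weight of the point.

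**Holm already protects.** It makes a false selection rare, but it does not remove the optimism once something is selected. With no signal, the excess given selection was 26 to 29 points with Holm and 22 to 27 without it (10 or 20 candidates).

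**The simulated pipeline is only partly the plan's.** Logistic regression, the multiple-regression screen and the non-linear screen were not simulated. The candidate counts are a reading of scattered lists, and gender and race are not normal variables. This stands: the direction is secure, but the percentages depend on the assumptions.

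**A corrected figure from 20 subjects says little.** Its between-study standard deviation is about 14-19 points at rho 0.5-0.7. That is true, but a noisy figure with little bias is less misleading than a noisy figure that reads high.

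**Stronger readings that the documents and the check do not support**
- A reader might infer that every accuracy computed from these subjects is inflated. That does not follow: nested leave-one-out uses the same subjects and is close to the truth for rho 0.5-0.9.
- A reader might equally infer that nesting removes the bias whenever a real predictor exists. At rho 0.3 it still reads about 5 points high.
- A reader might infer that the trial's effectiveness result is compromised, or that the cited 89.3% is itself inflated. The repeated-measures comparison does not use the classifier, and the documents do not show how the 89.3% was validated.

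**Conclusion.** The point holds as a gap in the exploratory prediction analysis that should be closed before analysis. The plan selects and classifies in the same 20 or fewer subjects and provides no validation. If resubstitution accuracy is reported, it will on average be too high whenever a predictor is selected. The excess is largest when the signal is weak or absent and smallest when it is strong. Leave-one-out applied only after the screen is an adequate remedy only if the signal is strong (rho about 0.7 or more).

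The sizes rest on the stated assumptions, none of which the plan fixes. The conclusion concerns resubstitution accuracy, and it matters only if such an accuracy is reported. It does not touch the comparison of NOSE and VAS between baseline and 90 days.

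**What to change.** Add to section 4.9:

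1. Any classification accuracy will be estimated by leave-one-subject-out cross-validation, with the whole pipeline, including the Holm screen, repeated inside each fold.
2. The candidate variables and the category cut-offs are listed in advance. So is the rule for a fold in which nothing passes; the choice between two simple rules moved the nested accuracy by at most 1.3 points.
3. If the full-data screen selects nothing, that is reported and no accuracy is given.
4. The nested accuracy is shown beside the majority-class rate and labelled exploratory.
5. For the outcome-prediction aim, the 90-day category is classified from pre-treatment predictors. If both visits are used, a subject's two records stay in the same fold.

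The cost is SAP wording and a few lines of code, with no extra patients, visits or measurements. The downside is a lower and noisy quoted accuracy. Some upward bias also remains when the signal is weak: about 5 points at rho 0.3 and 6-8 with no real predictor. It remains because an accuracy is reported only when the full-data screen, which uses every subject, has selected something. The report should say so.

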2.0 OVERALL OBJECTIVES

The study will evaluate the outcome of nasal obstruction treated with the Vivaer™ Stylus, and also attempt to use computational aerodynamics simulation and sensory measurements to identify and predict patients' treatment outcome. The ability to envisage variables that will lead to best outcome may have potential to assist patients and clinicians in planning effective, well-informed, personalized treatment/surgery strategies.

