4.3 Inclusion Criteria

Eligible subjects will meet all the following:

1. Age 18 to 75 years (inclusively)
2. Willing and able to provide informed consent
3. Willing and able to comply with the subject-specific requirements outlined in the study protocol
4. Complaints of nasal obstruction for at least 1 year
5. Failed maximum medical therapy (4-6 weeks of steroids)
6. Nasal Obstruction Symptom Evaluation (NOSE) score of ≥ 60 at Baseline
7. Nasal valve is a primary or significant contributor to the subject's nasal obstruction as determined by the study investigator (based on clinical presentation, physical examination, nasal endoscopy, etc.) and the subject has a positive response to any of the following temporary measures (based on patient history or during office exam):
 - a. Use of external nasal dilator strips (e.g., Breathe Right Strips)
 - b. Q-Tip test (manual intranasal lateralization)
 - c. Use of nasal stents
 - d. Cottle Maneuver (manual lateral retraction of the cheek; see Figure 4)

[figure not shown]

Figure 4. Cottle Maneuver

Figure 4 demonstrates the Cottle Maneuver as the patient or the physician temporarily lifts and laterizes the skin around the nose and cheek, increasing the nasal valve angle, and potentially increasing nasal airflow. A positive response can be an indicator that the patient will respond well to an increase in nasal valve angle.

The Q-Tip test is another evaluation of potential positive response. A Q-tip is placed gently within the nares against the lateral nasal wall at the location of the narrowest nasal valve region and is pushed outward lightly to expand the nasal valve angle. A positive response to this maneuver may also predict the potential benefit of nasal valve correction.

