For those potential candidates who agree to participate in the study by signing the IRB approved Informed Consent Form (ICF), a baseline evaluation will be conducted. Subjects will be considered enrolled once they arrive at the study clinic to undergo the procedure. At this time a subject identification number will be assigned along with the subject binder.

During the baseline and follow-up visits, the procedures listed below will occur

1. Endoscopic examination (video and pictures), Lund-Kennedy endoscopic scores
2. Peak nasal inspiratory flow
3. Cone beam CT scan (clinical CT at baseline; clinical or research CT at 90-day follow-up visit)
4. Nasal Obstruction Symptom Evaluation (NOSE) scale
5. Sino-Nasal Outcome Test (SNOT-22)
6. Visual analogue scale (VAS) rating severity of nasal obstruction
7. Computational modeling of nasal airflow based on CT scan of each visit.

During the baseline visit, data collection will be performed first, and then the Aerin Vivaer™ Treatment will be provided in the clinic by the physician. The styluses used in this study will be manufactured and supplied by the sponsor.

During the treatment, 0.5 ml of local anesthesia (lidocaine 1% with epinephrine 1:100,000) will be injected into the target tissue. The Vivaer stylus will be inserted into the nose and the electrode-containing tip will be positioned against the target tissue.

Subjects will have both nasal valves treated in a single study procedure session. Each nostril will be treated at up to 3 non-overlapping positions along the upper lateral nasal valve region.

Treatment settings to be used are:

Temperature.....60°C
Power 4 Watts
Treatment Time 18 secs
Cooling Time 12 secs

Accurate positioning will be confirmed by observing the temperature change on the RF generator screen as the stylus tip comes in contact with the target tissue.

No repeat ("touch-up") procedures will be permitted during the 90-day follow-up period.

Immediate Post-Procedure Care (prior to leaving the clinic)

At the discretion of the physician, the following care and instructions may be provided:

- Apply petroleum jelly to the treatment area as needed.

- The patient should be instructed not to manipulate the treatment site for 24 hours with the exception of any necessary hemostasis.

Study subjects will be reminded of their next follow-up visit and will be scheduled within the study window (90 ± 15 days).

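### The aim of predicting treatment outcome has no analysis of its own: section 4.9 classifies symptom categories without limiting predictors to pre-treatment values or naming the visit

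*Combined protocol and SAP*

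**What the plan says.** Section 2.0 sets two aims. The first is to evaluate the outcome of treatment. The second is to use airflow simulation and sensory measurements to "identify and predict patients' treatment outcome", with the stated hope of helping in "planning effective, well-informed, personalized treatment/surgery strategies".

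Section 4.9 describes the modelling in two steps. Spearman correlation and multiple regression are used to "screen for independent variables that significantly correlate with dependent variables", with a Holm-Bonferroni correction. Linear discriminant analysis and logistic regression are then applied for "classification and discrimination of patient symptom categories (e.g., symptom-free, moderate and severe nasal obstruction) based on significant independent variables". Neither step states the visit of the predictors, the visit of the category, the instrument or cut-offs behind the category, the unit of analysis, or how two records from one subject are handled.

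Two other parts of the plan bear on this:
- Section 4.3 requires a "Nasal Obstruction Symptom Evaluation (NOSE) score of ≥ 60 at Baseline".
- Section 4.7 lists, for both the baseline and the follow-up visit, "Computational modeling of nasal airflow based on CT scan of each visit". Peak nasal inspiratory flow (PNIF), endoscopic scores and CT are also obtained at both visits.

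**The concern.** A prediction meant for treatment planning can use only what is known before treatment, and its target must be what happens afterwards. Section 4.9 secures neither. Day-90 CFD, PNIF, endoscopy and CT values are not excluded as predictors, and the target is a symptom category rather than day-90 status or response.

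The entry criterion sharpens the problem. With everyone at NOSE 60 or more at baseline, the example range from symptom-free to severe cannot be filled from baseline records if the categories are patient-level and based on NOSE. An analyst would have to use day 90 alone or combine the visits. Day 90 alone gives a concurrent classifier. Combining visits also confounds symptom category with visit. Either result could be reported as meeting the section 2.0 aim, although neither shows that a pre-treatment measurement predicts who benefits.

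**Working it through.** The plan states no power, alpha or sample-size derivation, so there is no figure to reproduce. The check has a logical part and a simulation.

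**1. Inputs from the document.** Up to 20 subjects (4.2); two test sessions per subject (4.1); NOSE at least 60 at baseline (4.3); CFD, PNIF, endoscopy and CT at both visits (4.7). This gives at most 20 records per visit, or 20 × 2 = 40 if pooled.

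**2. Which visit can supply a symptom-free record?** For any NOSE cut-off below 60, the baseline count is 0 of 20. Every symptom-free record is therefore post-treatment. Moderate and severe records can occur at either visit.

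**3. Is a shift in the predictors between visits plausible?** Yes. Section 3.0 says that treatment lowers nasal airflow resistance, so simulated resistance should move with visit, and so should NOSE if treatment works.

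**4. Simulation of a variable with no within-visit relation to symptoms.** The predictor is x₀ ~ N(0,1) at baseline. At day 90 it is x₁ = ρx₀ + √(1−ρ²)·e, with e ~ N(0,1), shifted by δ standard deviations in the direction of improvement. NOSE is drawn independently of x at each visit. Everything apart from n = 20, two visits and the NOSE floor of 60 is assumed; none of it is in the documents. There were 3,000 to 4,000 runs per setting.

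Share of runs in which the pooled Spearman test gave p < 0.05:

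| Assumed inputs | δ = 0.5 | δ = 0.8 | δ = 1.0 | Baseline x against day-90 NOSE |
|---|---|---|---|---|
| Baseline NOSE truncated at 60; day-90 mean 30 to 45, SD 20; ρ = 0.6 | 16–20% | 38–51% | 56–75% | 4.3–5.5% |
| Baseline mean 75, SD 10, limited to 60–100; day-90 mean 25 or 40, SD 22; ρ = 0.5 | 17–21% | not run | 61–73% | 4.4–5.7% |

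In the first row the mean pooled Spearman correlation was 0.18 to 0.39. With δ = 0 the pooled rate fell to about 1–3%, so the excess comes from the visit difference.

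**5. Effect of the planned correction.** The documents give no number of tests. For an assumed 10, the first Holm threshold is 0.05/10 = 0.005. With baseline NOSE from a normal distribution (mean 70, SD 15) truncated to 60–100, and the other inputs as in the first row, the pooled screen passed the null variable in about 2.5% to 33% of runs for δ from 0.5 to 1.0, against a nominal 0.5%. With baseline mean 75 and SD 12 the range was about 2% to 36%.

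**6. Category against visit.** Under the second row, with symptom-free taken as NOSE below 25, the pooled AUC of the null variable for symptom-free was 0.58–0.60 at δ = 0.5 and 0.65–0.68 at δ = 1.0. Its AUC for visit itself was 0.64 and 0.76. Baseline x against day-90 category gave about 0.50, as it should.

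**7. Class sizes for a one-record-per-subject analysis.** If 20%, 35% or 50% are symptom-free at day 90 (assumed), the class has 20 × 0.20 = 4, 20 × 0.35 = 7 or 20 × 0.50 = 10 subjects.

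**The case against.** The strongest reply is that the classifier is being held to the wrong aim. Section 4.9 states a mechanistic hypothesis, that airflow and cooling at the nasal valve govern perceived patency. It cites earlier work that classified subjects' ratings with 89.3% success. Relating CFD to symptoms at the same visit tests that directly. Section 2.0 words the prediction aim modestly: the study will "also attempt to use computational aerodynamics simulation and sensory measurements to identify and predict" outcome. This stands, and a reader who infers that the concurrent classifier is a wrong analysis goes too far. But it leaves the second aim unserved, because the cited result concerns ratings, not response to treatment.

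A reader might also infer that the plan pools baseline and day-90 records. It does not say so. Its wording equally fits an analysis within day 90, or one of baseline predictors against day-90 outcome. The simulated error rates therefore describe a conditional risk.

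It is also tempting to say that the pooled model would simply classify visit, or that symptom-free cannot exist before treatment on any definition. Neither is supported. Moderate and severe can occur at both visits. The categories are given only as examples, without instrument or cut-offs, and section 4.6 records VAS for each nostril separately, so a side-level category could be clear at baseline.

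Finally, "The Holm Bonferroni correction will be applied to control for multiple comparisons", so the 0.05 rates alone overstate the risk. The adjusted rates are lower but still well above nominal.

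**Conclusion.** The point holds in this form: the section 2.0 prediction aim has no analysis that specifically answers it, because 4.9 neither restricts predictors to baseline nor fixes the outcome as day-90 status. That conclusion needs no simulation and does not depend on pooling, since a day-90-only classifier cannot guide planning either.

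The visit confounding is a further, conditional consequence. It requires pooled records and a patient-level NOSE-based category. Under the assumed shift of 0.5 to 1.0 SD, a variable unrelated to symptoms within either visit passes in roughly 16–75% of trials at 0.05, and in roughly 2–33% at 0.005. Relating baseline values to day-90 outcome keeps the rate near 5% at 0.05. These figures are illustrative, because the documents give no effect sizes.

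This is an exploratory part of a single-arm series of up to 20 subjects. The before-after comparison of treatment effectiveness is not affected. The change should be made, but it does not call the whole study into question.

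**What to change.** Separate the two questions in section 4.9.

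1. **Prediction (the section 2.0 aim).** Use only baseline variables as predictors: CFD, PNIF, endoscopic and CT scores, demographics and history. Take day-90 outcome as the dependent variable, either day-90 NOSE adjusted for baseline NOSE or a day-90 symptom category. State the instrument and cut-offs in advance. Use one record per subject.
2. **Explanation (the 4.9 hypothesis).** Label any analysis that uses post-treatment CFD as explanatory. Run it within day 90, or include both visits with visit and within-subject correlation in the model. Do not treat the baseline and day-90 records of one subject as independent.

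The cost is wording in 4.9; no new data or visits are needed. The downside is that the prediction analysis has at most 20 records rather than 40, so some classes may be very small and the classifier will look less impressive. That limit should be stated.
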